“Cognitive behavior therapy for work success in veterans with mental illness: A pre-post efficacy study”

Study Protocol and Statistical Analysis Plan

ClinicalTrials.gov Identifier: NCT01918774

Principal Investigator: [name]., HSPP

Version date: 2/26/2016

Overview of the Problem

In 2010, 11.5% of all Gulf War-II veterans were unemployed; that figure rose to 15.2% in January 2011 and continues to grow as the number of veterans from recent wars increases (United States Department of Labor, 2011; Seal et al., 2009). The prevalence of mental illness among veterans is also notable; estimates range from 31% (Seal et al., 2007) to nearly 37% (Seal et al., 2009) for any psychiatric disorder, and over half of these veterans are diagnosed with more than one psychiatric condition (Seal et al., 2007). In addition, empirical evidence suggests that some mental disorders are more prevalent in veterans than in the general population (Kessler et al., 2005). Linking unemployment and mental illness, a recent study found that 65% of veterans using VA healthcare were unemployed, and compared to employed veterans, the unemployed were more likely to have depression, bipolar disorder, post-traumatic stress disorder (PTSD), schizophrenia, or substance use disorders. Vocational dysfunction was reported most often in disabled veterans with schizophrenia, PTSD, and substance use disorders (Zivin et al., 2011). Not surprisingly, this study also found that unemployed veterans had significantly lower income than employed persons. Similarly, a large study focusing specifically on veterans with PTSD concluded that vocational dysfunction is a notable problem among this group, as they were significantly less likely to be employed after participating in VA work programs compared with participants without the disorder (Resnick & Rosenheck, 2008). Because most individuals with mental illness desire to work in regular competitive employment (McQuilken et al., 2003), the nationwide problem of unemployment among veterans with mental illness is particularly troubling.

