Rationale: Cognitive behavioral therapy (CBT) effectively reduces symptoms across a range of psychiatric conditions (Butler et al., 2006; Wykes et al., 2008); however, its benefit to functioning remains less well understood. Some studies have evidenced a positive influence of CBT on functional outcomes, whereas others have not. One possible explanation for these inconsistencies across studies is that CBT interventions are most often focused on symptoms rather than community functioning. The few CBT interventions that have been specifically designed to address functioning have shown promising results. One functional area of critical importance is work—a central goal of most veterans with (and without) mental illness. However, work functioning has received little empirical attention in the CBT domain. Despite research evidence suggesting that maladaptive thoughts about oneself and expectations about the ability to work interfere with work success (e.g., Hoffman et al., 2000; Kukla, Bonfils & Salyers, 2015; Kukla, McGuire, & Salyers, 2015), no CBT programs have been developed specifically targeting vocational themes with the goal of improving competitive work outcomes. Further, a recent paper outlined needed avenues of future study in the SE domain; Drake and Bond (2011) state that cognitive strategies may be a fruitful area to develop to help “nonresponder” consumers with mental illness who struggle with vocational dysfunction despite high quality vocational assistance. The goal of the current project is to address this gap and the serious problem of unemployment in veterans with mental illness by pilot testing the CBT for work success program (CBT_w) and assessing key employment outcomes before and after the intervention.

Overall Design:

Adult participants will take part in the 12 week CBT_w program. All participants will receive standard SE services during the study. The longitudinal design will consist of assessments of competitive employment outcomes, important psychosocial outcomes, and background and demographic variables at baseline and at two follow-up periods—immediately following the conclusion of the CBT_w program (12 week follow up point) and at a 6 month follow up. The 6 month follow up period is exploratory.

Setting and Participants:

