Next, the primary study outcome of weeks worked during the baseline period (6 months preceding baseline) and the 6 months study period will be compared using dependent groups (paired samples) t-tests. Significance values for t-tests will be set at $p < .05$. The secondary work outcome, attainment of steady competitive work will be characterized using percentage of total participants achieving this benchmark. Because secondary outcomes are exploratory, these will be characterized using descriptive statistics, such as means and standard deviations.

Missing Data:

To address the issue of missing follow-up data, participants' baseline characteristics will be compared between those with and without missing data. We will also fit a logistic regression model to compare intervention and control participants with missing outcome data to determine whether missing data is completely at random. If not random, we will perform the analysis with complete cases, using LOCF imputation method. Multiple imputation techniques will be used to evaluate the robustness of our analysis for the main outcome.

References

- Albert, K.A., & Luzzo, D.A. (1999). The Role of Perceived Barriers in Career Development: A Social Cognitive Perspective. *Journal of Counseling & Development, 77*, 431-436.
- Americans with Disabilities Act of 1990, Pub. L. No. 101-336, § 2, 104 Stat. 328 (1991).
- Anthony, W.A. (1993). Recovery from mental illness: The guiding vision of the mental health service system in the 1990s. *Psychosoc Rehabil J, 16*(4), 11-23.
- Arns, P. G., & Linney, J. A. (1993). Work, self, and life satisfaction for persons with severe and persistent mental disorders. *Psychosocial Rehabilitation Journal, 17*(2), 63-79.
- Attkisson, C. C., & Zwick, R. (1982). The client satisfaction questionnaire. Psychometric properties and correlations with service utilization and psychotherapy outcome. *Eval Program Plann, 5*(3), 233-237.

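### The missing-data rule compares missingness with a control arm this single-arm study does not have, and its fallback joins complete cases with LOCF, which does not suit a cumulative six-month total of weeks worked

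*Combined protocol and SAP*

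**What the plan says.** The title describes "A pre-post efficacy study", and Overall Design says: "Adult participants will take part in the 12 week CBT_w program. All participants will receive standard SE services during the study". Procedures assigns participants only to CBT_w groups. A randomized trial appears in the SAP only as future work.

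The SAP's primary analysis is a paired t-test of "weeks worked during the baseline period (6 months preceding baseline) and the 6 months study period". Under Missing Data it lists four steps:

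1. "baseline characteristics will be compared between those with and without missing data".
2. The analysts will "fit a logistic regression model to compare intervention and control participants with missing outcome data", to judge whether data are missing completely at random.
3. "If not random, we will perform the analysis with complete cases, using LOCF imputation method".
4. "Multiple imputation techniques will be used to evaluate the robustness of our analysis for the main outcome".

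Competitive Employment Outcomes (Study Measures) adds that weeks worked come from self-report and, where they can be had, supported employment records.

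**The concern.** Step 2 needs two arms and the study has one. It is the plan's named test of whether data are missing completely at random, and its result triggers step 3. The plan does not say that the baseline comparison in step 1 takes over as the trigger.

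Step 3 names two analyses that exclude each other: dropping incomplete records and filling them in. If LOCF alone was meant, the value to be carried is not stated, and the outcome is of the wrong kind for it. LOCF takes a score seen at one visit as standing at the next. Weeks worked over six months is a sum that can only grow after each visit, so an earlier count is part of the total and not an estimate of it.

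This bears on the primary outcome, which is the only one with a planned significance test. Missing follow-up is foreseeable, since Privacy/Confidentiality Issues tells participants they may leave at any time or skip questions. As written, the handling would have to be chosen once the data are in hand.

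**Working it through.** The documents give no sample size, drop-out rate or standard deviation here, so there is no stated figure to reproduce. The checks below show what the rule does.

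**Arm comparison.** If everyone is in one arm, the arm variable is constant. A design matrix of intercept plus arm has two columns but rank 1, so an arm coefficient cannot be estimated. Steps 1 and 4 need no second arm.

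**Inputs from the documents.** Assessments are at baseline, post-intervention and six months (Overall Design). Both steadily employed and job-seeking veterans are eligible (Setting and Participants). A group starts only once eight veterans are enrolled (Procedures), so the post-intervention visit can fall later than 12 weeks after baseline.

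**Assumptions.** The six months are T = 26 weeks counted from baseline. The visit is at V = 12 + g weeks, with a wait g of 0, 4 or 8 weeks. Twenty per cent of the sample lack six-month data, half like veteran A and half like veteran B:

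- Veteran A is employed throughout: b = 26 baseline weeks, c = V weeks worked by the visit, true change 0.
- Veteran B has b = 0, c = 6, and is employed at the visit. With no wait, the true change lies between +6 and +20.

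**Change scored under each reading of LOCF.**

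- Baseline total carried: b − b = 0.
- Count carried: c − b.
- Rate extended: (c/V) × T − b.
- Status extended (employed at the visit): c + (T − V) − b.

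For A, the count reading gives V − 26: 12 − 26 = −14, 16 − 26 = −10, 20 − 26 = −6. The other three readings give 0.

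For B, the baseline reading gives 0 and the count reading +6. The rate reading gives 6/12 × 26 = 13, 6/16 × 26 = 9.75 and 6/20 × 26 = 7.8. The status reading gives 6 + 14 = 20, 6 + 10 = 16 and 6 + 6 = 12. Carrying the baseline total scores B at 0 although six weeks of work have already been observed.

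**Contribution to the mean change in weeks**, 0.20 × (A + B)/2:

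| Wait g | Baseline | Count | Rate | Status | Baseline v count | Full spread |
|---|---|---|---|---|---|---|
| 0 | 0 | 0.2 × (−14 + 6)/2 = −0.8 | 0.2 × 13/2 = +1.3 | 0.2 × 20/2 = +2.0 | 0.8 | 2.8 |
| 4 | 0 | 0.2 × (−10 + 6)/2 = −0.4 | 0.2 × 9.75/2 = +0.975 | 0.2 × 16/2 = +1.6 | 0.4 | 2.0 |
| 8 | 0 | 0.2 × (−6 + 6)/2 = 0 | 0.2 × 7.8/2 = +0.78 | 0.2 × 12/2 = +1.2 | 0 | 1.2 |

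The 0 at an eight-week wait arises because A's −6 and B's +6 cancel in this mix. It does not show that either reading is unbiased.

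**The case against.** The strongest reply has four parts.

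- **The regression is nearly an editorial slip.** It estimates no outcome, step 1 does a similar job in one arm, and a reworded sentence repairs it. This stands: that part has no direct effect on the primary estimate.
- **LOCF has a plain meaning, the last observed value.** On that view, extending a rate or a status is extrapolation, and carrying baseline for someone with a later count is a different method. This stands in part. The Missing Data text does not point to the rate or status readings, so the fair contrast is count against baseline. But the plain meaning still credits no work after the last contact, and it leaves the conflict with complete cases unresolved.
- **The harm is conditional.** The clause applies only if data are judged not random, every participant is enrolled in supported employment, whose records may supply the weeks, and multiple imputation is planned. This limits the harm. It does not settle the main analysis, because the imputation is a robustness check on an analysis that is itself undefined.
- **The arithmetic depends on when the six months start.** The SAP's description of a six-month study period favours counting from baseline, but no section fixes it. If the period ran from the end of the program, the post-intervention count would lie outside it and the figures would not apply. This stands.

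A reader might infer that the whole missing-data plan collapses. It does not: steps 1 and 4 can be run in one arm. A reader might also infer that step 3 cannot be carried out at all. It can once someone chooses a meaning; the fault is that the text contradicts itself and that LOCF does not suit this outcome.

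**Conclusion.** The point holds. The arm comparison cannot be fitted, which is minor on its own. The fallback for the primary outcome is contradictory, and each literal LOCF reading builds in an assumption: no later work if the count is carried, or no change if the baseline total is carried. It should be fixed before analysis.

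The size for this study is unknown. In the illustration, one continuously employed veteran is scored 14, 10 or 6 weeks too low when the count is carried, for waits of 0, 4 or 8 weeks. At group level the two readings closest to literal LOCF differ by 0.8, 0.4 or 0 weeks. These figures rest on 26 weeks counted from baseline, 20% missing and an invented half-and-half mix.

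A reader might take the 2.8-week spread in the table as the likely error in the primary result. The documents do not support that: it needs the status reading, no wait and this particular mix, and the same calculation with an eight-week wait gives 1.2.

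**What to change.** - Replace the arm comparison with a model of missing six-month weeks (yes/no) on a few baseline variables, such as work status and weeks worked.
- Delete the clause on complete cases and LOCF. Do not carry a 12-week or baseline count forward as the six-month total.
- State when the six months start.
- Fill missing weeks from supported employment records where available. Then make the multiple imputation already planned the main method, with a small model: baseline weeks, baseline work status, and weeks worked to the post-intervention visit where observed.
- Impute the proportion of remaining weeks worked, between 0 and 1, and multiply by each person's remaining weeks, so that totals stay between the weeks already observed and 26. Imputing raw later weeks can break that limit: 14 weeks borrowed from someone seen at week 12, given to someone seen at week 20 who has worked 20 weeks, make 34.
- Report complete cases beside it, with two labelled drop-out scenarios: no further work, and continued work, after last contact. With no wait, veteran B would score +6 and +20 under these.

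The cost is SAP wording and slightly more analysis; the imputation and the records are already in the plan. The downside is that the primary result would rest on a small imputation model in a possibly small sample, which is why the complete-case result and both scenarios must be shown with it.

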Inclusion criteria is a diagnosis of any mental disorder as confirmed through medical record review; common diagnoses include schizophrenia, bipolar disorder, PTSD, personality disorders, anxiety disorders, and depressive disorders. Second, participants must be enrolled in VA supported employment services. Third, participants must also have an active goal of working in the community; participants can be currently working in the community or unemployed and searching for work. Both veterans seeking employment and those currently employed will be eligible for the pilot study in order to enhance the external validity of our findings. That is, people with mental illness commonly move in and out of job search and job maintenance phases over time and our findings will apply to the average veteran receiving SE services. In addition, including veterans in steady employment as well as those who are searching for a job (and may be experiencing more vocational instability) will reduce selection bias. In other words, we are not limiting our sample to only those veterans who are highest functioning with the greatest work ability.

Exclusion criteria is a major cognitive deficit or severe medical condition that would prevent participation in the intervention and/or community work.

Intervention:

The CBT_w program includes 12 sessions that are delivered in a weekly one-hour group format. Sessions focused on identifying and modifying maladaptive thoughts related to work, enhancing self efficacy and beliefs in one's ability to succeed at work, identifying and addressing personal barriers to work, and increasing beneficial coping strategies that can be applied across employment settings, including during the job search phase and working on the job. The intervention is tailored toward both employed and unemployed persons seeking community work. Session content includes the following modules: Introduction—Work goals and work story; CBT model and work; Thinking about work; Barriers to work; Coping with stress and anxiety; Coping with anger and difficult emotions; Communication at work; Dealing effectively with people at work; Managing work success; Personal work success plan.

Procedures:

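### The rule for non-random loss names two incompatible methods, complete cases and LOCF, and neither is generally valid in that situation

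*Combined protocol and SAP*

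**What the plan says.** The Statistical Analysis Plan has one significance test. Weeks worked in the six months before baseline and in "the 6 months study period will be compared using dependent groups (paired samples) t-tests", at the 0.05 level.

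The Missing Data section plans two checks. In the first, "participants' baseline characteristics will be compared between those with and without missing data". The second reads "We will also fit a logistic regression model to compare intervention and control participants with missing outcome data", and its stated purpose is "to determine whether missing data is completely at random".

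The rule that follows is "If not random, we will perform the analysis with complete cases". The sentence does not end there: after a comma it names LOCF as the imputation method. The section then adds: "Multiple imputation techniques will be used to evaluate the robustness of our analysis for the main outcome". No condition is attached to that last step and no imputation model is given. No method is stated for loss found to be random.

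Three other places bear on the point:
- Overall Design describes one group, all of whom receive the programme.
- Under Setting and Participants, "participants can be currently working in the community or unemployed and searching for work".
- Under Study Measures, the employment outcomes come from self-report and, when available, from supported employment (SE) records.

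**The concern.** Complete-case analysis drops veterans without a follow-up value. LOCF keeps them and supplies one. A single analysis cannot do both, and the text does not say which is meant, or which value LOCF would carry into a six-month count of weeks.

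Either reading is weak in the branch where it applies. That branch is entered only after completely random loss has been rejected, and an unadjusted paired t-test on completers does nothing to correct for differences between retained and lost veterans.

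Such differences could plausibly matter here. The outcome is bounded by the length of the window: a veteran with no weeks worked before baseline cannot fall, and one who worked throughout cannot rise. Change is therefore tied to baseline employment, and the study enrols both employed and unemployed veterans. If one group is lost more often, the mean change among completers moves. What is at stake is the primary estimate and its p-value, and also the means and standard deviations that the plan intends to use in sizing a later randomized trial.

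**Working it through.** **Inputs.** The documents give no sample size, dropout rate, standard deviation or expected change, so there is no figure of the plan's to reproduce. Every number below is an assumption chosen for illustration.

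**General result.** Let m be the fraction missing, Dobs the mean change in those observed and Dmis the mean change in those missing. Then:
- true change = (1 - m) × Dobs + m × Dmis
- complete-case bias = m × (Dobs - Dmis)
- bias with baseline weeks carried forward (change set to 0) = -m × Dmis

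Complete cases are unbiased when the lost and the retained have the same mean change. Baseline carried forward is unbiased only when the lost had no change on average.

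**Illustration.** Assume 60% unemployed at entry with mean change +6 weeks, and 40% employed with mean change -4 weeks. True mean = 0.6 × 6 + 0.4 × (-4) = +2.0.

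Loss of 40% of unemployed and 10% of employed:
- Retained shares: 0.6 × 0.6 = 0.36 and 0.4 × 0.9 = 0.36, total 0.72.
- Complete cases: (0.36 × 6 - 0.36 × 4) / 0.72 = 0.72 / 0.72 = +1.00.
- Baseline carried forward: 0.36 × 6 - 0.36 × 4 + 0.28 × 0 = +0.72.

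Losses swapped:
- Retained shares: 0.6 × 0.9 = 0.54 and 0.4 × 0.6 = 0.24, total 0.78.
- Complete cases: (0.54 × 6 - 0.24 × 4) / 0.78 = 2.28 / 0.78 = +2.92.
- Baseline carried forward: +2.28.

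The same formulas across a range of losses, against a true +2.0:

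| Loss: unemployed / employed | Complete cases | Baseline carried forward |
|---|---|---|
| 40% / 10% | 1.00 | 0.72 |
| 10% / 40% | 2.92 | 2.28 |
| 30% / 10% | 1.08 / 0.78 = 1.38 | 1.08 |
| 10% / 30% | 2.12 / 0.82 = 2.59 | 2.12 |
| 25% / 25% | 1.50 / 0.75 = 2.00 | 1.50 |

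In every row, weighting the two observed group means by their shares at entry returns 0.6 × 6 + 0.4 × (-4) = 2.0, because loss here depends only on employment at entry. Imputation that includes baseline employment aims at this quantity. The last row shows baseline carried forward biased even when loss is unrelated to employment.

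**Limit of imputation.** A separate simulation drew weeks in the two windows as correlated normals (means 8 and 12, SD 9, correlation 0.4), limited them to 0-26 and lost 25% of follow-up values. Regression on baseline weeks stood in for multiple imputation. The true change was 3.32.
- When veterans with low baseline weeks were lost more often, complete cases gave 2.65, baseline carried forward 1.99 and imputation 3.32.
- When loss depended on a covariate unrelated to change, complete cases gave 3.32, with no bias.
- When veterans with low follow-up weeks were lost more often, complete cases gave 4.20, baseline carried forward 3.15 and imputation 4.50. Imputation on baseline alone does not repair this last case.

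**The case against.** A reader who stops at the comma might infer that the trigger simply runs backwards, with complete cases reserved for the situation in which they fail. The full sentence does not support that. If LOCF is the operative method, the non-random branch does impute, though poorly, and the fault is a contradiction plus a weak method. The numbers depend on the reading: with the losses swapped, the bias is +0.92 for complete cases but +0.28 for baseline carried forward.

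A reader might also infer that the primary result would be biased whenever the check is positive. It would not. Rejecting completely random loss shows only that bias is possible, and it is zero if loss is unrelated to change in weeks. The unconditional multiple imputation also means that a biased result would not stand alone.

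Nor do the documents show that a low-powered check leaves the choice of method to chance. The logistic check cannot be run in a single-arm study, and the baseline comparison has no stated variables, test or threshold, so no firing rate can be derived. No other method is given for random loss, and a paired t-test drops incomplete pairs anyway. On the complete-case reading, the trigger would change nothing.

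These points limit the concern without removing it. The sentence is still contradictory, and neither method it names is generally valid where it applies. The robustness check has no specified model and does not determine the primary p-value.

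**Conclusion.** The concern holds in this form: the rule for non-random loss is contradictory, both of its methods can bias the primary estimate, the method better suited to loss explained by measured baseline variables is secondary, and the logistic check feeding the rule needs a comparison group that does not exist.

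Under the assumed inputs, with losses of 40% and 10%, the error runs from -1.28 to +0.92 weeks on a true change of +2.0. With losses of 30% and 10% it runs from -0.92 to +0.59. These figures show direction and plausible scale only. They assume that loss depends on employment at entry, that change differs by 10 weeks between the two groups, and that LOCF carries baseline weeks forward. None of this is in the documents, and the true size is unknown. Confidence is medium. The point should be fixed, because it concerns the only significance test and the remedy uses data and methods already planned.

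**What to change.** Delete the non-random trigger, the LOCF clause and the reference to control participants. Keep the baseline comparison as description only. Suggested replacement:

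*Whatever the missingness comparison shows, weeks worked will first be taken from supported employment records where these are available. For weeks still missing, the main estimate of change will use multiple imputation (or an equivalent likelihood-based model) with baseline weeks worked, baseline employment status and 12-week employment data as predictors. Imputed weeks will be limited to the length of the window. Complete cases will be reported as a sensitivity analysis, together with an analysis that shifts the imputed weeks up and down over a stated range.*

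SE records come first because they are a source of the outcome itself: where they cover the window, a missed interview need not mean a missing value. The shifted analysis addresses loss that depends on unobserved follow-up weeks, which imputation from measured variables cannot correct.

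The cost is SAP wording, a little more analysis work and possibly a slightly wider interval. Multiple imputation is already planned, and baseline work status and prior weeks worked are already collected.
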